The Implementation of EIT-4-BPSD: [name] will train the Research Nurse Facilitators on how to best work within each intervention facility so that implementation is culturally sensitive to the diversity within each site. To guide assessment of residents and the development of staff training materials she will use seven key elements from the literature¹²⁶⁻¹²⁸: communication, space, social orientation, time, environmental control, biological variations and trust. This training helps to ensure a participatory implementation approach as delineated in the EIT³⁰. Facilities voluntarily participate and identify a Champion and Stakeholder Team members. We will recommend the following stakeholders as part of the implementation process: a nurse in a leadership position (e.g., director of nursing); a unit nurse; a nursing assistant; a family member; an activity staff; a social worker; and a resident. As per facility preference, other team members can also be included. All EIT-4-BPSD related activities will be done during scheduled working hours for the facility employed stakeholders. EIT-4-BPSD is implemented by the Research Nurse Facilitator working with the Champion and Stakeholders using our 4-step approach. EIT-4-BPSD involves a combined face-to-face and an internet enhanced approach that includes ongoing, iterative, and active participation of all Stakeholders. The Research Nurse Facilitator will arrange the first face-to-face meeting with the Champion and Stakeholders in each facility. This meeting introduces the Stakeholder Team to the participatory process and their responsibilities, and will provide training on the knowledge and skills they will need for implementation. It will be scheduled for 4 hours (Table 1); Appendices A, B, C and the Nursing Home Toolkit contain the training materials.

Table 1: Content for First EIT-4-BPSD Meeting With the Stakeholder Team

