Procedure for Assessing Outcomes: Facility-level and resident-level outcomes will be obtained by trained research assistants (RAs) who are blind to facility condition (treatment versus control). To maintain blinding, these RAs will not be provided with information about randomization or details of the different interventions and we will keep all meetings of evaluation and intervention teams separate. Inter-rater reliability will be done on 10% of our outcome measures. Blinded RAs will obtain all resident descriptive and outcome data and descriptive facility data at baseline, 4 and 12 months from the following sources: designated administrative staff for facility relevant date (e.g., staffing); resident medical chart; and observations by the RAs and input

from the facility staff working with the resident at the time of evaluation (approximately 10 minutes of staff time). The Research Nurse Facilitator will obtain setting RE-AIM outcomes at baseline, 12 and 24 months in intervention sites only as delineated in Appendix E.

Measures are in Appendix F. Overview of each measure, measurement level, source of data, and timing of data collection are in Appendix E

Facility Descriptive Data

The following data will be obtained at baseline to describe facilities and consider confounders: state; size; profit or non-profit ownership status; urban or rural; Nursing Home Compare reported descriptives (11 outcomes such as percentage of residents with pain); staffing ratio and mix [at baseline, 4, 12 months: number of nursing assistants; nurses (registered; licensed practical nurses), and activity staff /number of residents].

Resident Descriptives

Resident descriptive information: age, race, gender, education, and marital status at baseline; psychotropics (antipsychotics, antidepressants, sedative/hypnotics, anxiolytics) obtained at baseline, 4 and 12 months.

Cognitive status will be measured at baseline using the Brief Interview of Mental Status (BIMS).¹²² The BIMS includes 3-item recall and orientation questions with scores ranging from 0 to 15. Prior use has provided evidence of reliability and validity.¹³²⁻¹³⁴

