Behavioral Symptoms (Effectiveness): Depressive symptoms will be measured using the *Cornell Scale for Depression in Dementia (CSDD)*^{139,140}. CSDD is a 19 item survey that assesses depressive symptoms in individuals with dementia. There is evidence of reliability and validity of the CSDD.¹³⁹⁻¹⁴¹ Aggressive and/or resistive behaviors during care activities will be measured using the *Resistiveness to Care Scale*,¹⁴² a reliable and valid 13 item Likert scale that assesses residents' behaviors during activities of daily living. Agitated

behaviors will be measured using the *Cohen-Mansfield Agitation Inventory (CMAI)*,^{143,144} a survey of disturbing behaviors commonly found in residents with dementia. The 14 item version CMAI uses a 5-point Likert scale to rate the frequency of behavioral symptoms.^{144,145} Prior use supported evidence of reliability and validity.^{144,145}

Function (Effectiveness): *The Barthel Index (BI)*¹⁴⁶ is a 10 item measure of performance of activities of daily living with evidence of internal consistency, inter-rater reliability and validity.^{146 147} Items are weighted to account for the amount of assistance required. A total score of 100 indicates complete independence.

Quality of Life: will be measured using the *Quality of Life-AD (QoL-AD)*¹⁴⁸ scale. The QoL-AD is a 13 item reliable and valid instrument designed to rate the resident's quality of life from the staff perspective. Examples of items include physical condition, mood, relationships and participation in meaningful activities. Ratings are obtained on a 4 point scale (1= poor to 4=excellent) and total scores range from 13-52.¹⁴⁸

Adverse Events (Effectiveness): will be based on data obtained from medical records and designated individuals within the facilities (e.g., quality assurance nurse). Adverse events will include falls and transfers to hospitals or emergency rooms and physical restraint use. Baseline will include the four months prior to treatment implementation; 4 month will include those between baseline and 4 months; and 12 month those that occur between 4 months and 12 months post implementation of the intervention. Restraint use will be based on the reliable Minimum Data Base 3.0 definition of assessment for use of restraints.¹⁴⁹⁻¹⁵¹

Data Analysis:

Aim 1: To implement and test the implementation of EIT-4-BPSD.

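### The RA blind does not extend to staff informants: QoL-AD, and other resident scales as far as they use staff input, may be rated by people delivering EIT-4-BPSD

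*Combined protocol and SAP*

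**What the plan says.** Procedure for Assessing Outcomes states: "Facility-level and resident-level outcomes will be obtained by trained research assistants (RAs) who are blind to facility condition (treatment versus control". It continues: "Blinded RAs will obtain all resident descriptive and outcome data and descriptive facility data at baseline, 4 and 12 months from the following sources". For residents the list includes the chart and the RAs' own observation. It also includes staff input, which is to come "from the facility staff working with the resident at the time of evaluation (approximately 10 minutes of staff time".

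The protection is aimed at the RAs: "To maintain blinding, these RAs will not be provided with information about randomization or details of the different interventions". Meetings of the evaluation and intervention teams are also kept apart. The source for each measure is referred to Appendix E, which is not part of the available text.

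Under Resident RE-AIM Measures, QoL-AD rates "quality of life from the staff perspective". Adverse event data "will be based on data obtained from medical records and designated individuals within the facilities (e.g., quality assurance nurse".

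Under Setting, the Champion must be an RN, LPN or CNA. Under The Implementation of EIT-4-BPSD, the recommended Stakeholder Team includes "a nurse in a leadership position (e.g., director of nursing); a unit nurse; a nursing assistant; a family member; an activity staff". Under Design, assignment is concealed only until the facility has consented.

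**The concern.** A blinded interviewer does not make a rating blind when the person answering knows the arm. In an EIT-4-BPSD home the caregiver on duty has been trained and may be coached by the Champion. That caregiver may also be the Champion or a team member, someone who sets facility goals and reviews progress each month. For the EO arm the plan describes staff education sessions, but no team, coaching or monthly review.

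The result for QoL-AD, and for any other scale that draws on staff input, can therefore mix change in residents with change in how staff rate them. Expectation would favour EIT-4-BPSD. Better recognition of BPSD after training would work against it. The trial is designed around a small effect, so even a modest rating shift matters.

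**Working it through.** **1. Who is covered by the blind.**

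| Question | What the plan gives | Where |
|---|---|---|
| Who is kept blind? | The RAs | Procedure for Assessing Outcomes |
| Who supplies resident data? | Chart, RA observation, staff on duty | Same section |
| Which scale is expressly staff-rated? | QoL-AD | Resident RE-AIM Measures |
| Source for CSDD, CMAI, Resistiveness to Care, Barthel? | Not assigned in the main text | Appendix E (not available) |
| Can a Champion or team member be the informant? | Not excluded | Setting; The Implementation of EIT-4-BPSD |
| Does the team know which residents are in the study? | Yes: it reviews consented residents' care plans in months 3 to 12 | Table 2 |

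**2. Whether the analysis removes a rating shift.** H1 is tested by the group-by-time interaction. Write b for the average informant shift in SD units. The expected interaction is then

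true effect + (b_EIT,post − b_EIT,baseline) − (b_EO,post − b_EO,baseline).

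A rater difference that is stable over time cancels. A shift that starts after training does not, assuming baseline is rated before training. Two other provisions do not help. In the inter-rater check on 10% of measures, two RAs hearing the same caregiver would agree. The only planned sensitivity analysis concerns dropout.

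**3. The plan's own figures, as a reference for size.** Inputs from Sample Size: d = 0.19, two-sided alpha 0.05, ICC 0.02, correlation between repeated measures 0.6, 500 evaluable residents, 50 homes, 20% attrition.

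- Recruitment: 500 / (1 − 0.20) = 625, which matches the plan.
- Design effect: 1 + (10 − 1) × 0.02 = 1.18.
- SE = √(v × 1.18 × 4 / 500), where v is the variance factor of the analysis used.
- Mean of two post-baseline visits adjusted for baseline: v = (1 + 0.6)/2 − 0.6² = 0.44, SE = 0.0644, power at 0.19 = 0.838. This agrees with the stated power of at least 0.80.

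The plan does not name its variant, so three other common ones are shown as a range. The sample size itself is not in dispute.

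**4. Size of an assumed shift.** 0.10 / 0.19 = 53% of the planned effect. For QoL-AD, with an assumed SD of 5 to 7 points, the planned effect is 0.19 × 5 to 0.19 × 7 = 0.95 to 1.33 points. A shift of 0.10 SD is 0.5 to 0.7 points: one category on one of the 13 items in about 50% to 70% of residents, net of baseline and of the EO arm.

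**5. Chance of a false significant benefit if the true effect is zero.** The probability is 1 − Φ(1.96 − b/SE), where b is the assumed shift in the estimated contrast, favouring EIT-4-BPSD.

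| Variant | v | SE | Power at 0.19 | b = 0 | b = 0.05 | b = 0.10 | b = 0.15 |
|---|---|---|---|---|---|---|---|
| Mean of two post visits, baseline-adjusted | 0.44 | 0.0644 | 0.838 | 2.5% | 11.8% | 34.2% | 64.3% |
| One post visit, baseline-adjusted | 0.64 | 0.0777 | 0.686 | 2.5% | 9.4% | 25.0% | 48.8% |
| Mean of three visits | 0.733 | 0.0832 | 0.627 | 2.5% | 8.7% | 22.4% | 43.8% |
| Change from baseline to 12 months | 0.80 | 0.0869 | 0.590 | 2.5% | 8.3% | 20.9% | 40.8% |

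A shift of the opposite sign would hide a real benefit instead. The documents give no bias sizes; all values of b are assumptions.

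**The case against.** The strongest reply has four parts.

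- **Scope.** The sentence that names staff input also names the chart and the RAs' own observation, and it does not assign sources to scales. Only QoL-AD is tied to staff. A reader might infer that the blind covers none of the H1 outcomes. The documents do not support that: psychotropic use is not a rating, adverse events come partly from records, and the mix of sources for the other scales is in an appendix that cannot be seen. This stands, and the point is limited accordingly.
- **Claim of blinding.** The plan says that the RAs are blind. It does not say that informants are, or that staff-rated results will be presented as blinded. This also stands; what is missing is an explicit statement of the limit.
- **Inherent to the design.** Residents score 0 to 12 on the BIMS and staff deliver a facility-wide intervention, so some input from aware staff is hard to avoid. True, but which staff member is asked, and when the chart is opened, can be chosen.
- **The exclusion is partial and uneven.** Other EIT-4-BPSD staff are also trained and coached. The recommended team is small, in homes of at least 100 beds, so team members may seldom be the informant; the plan gives no frequency. The rule would also remove more people in EIT-4-BPSD homes than in EO homes. These are fair limits on how much the exclusion achieves, and they are why the description of the scales must change too.

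On the chart, RAs are not told what the interventions contain, and regulatory pressure moves all homes toward person-centered care. A care plan therefore need not reveal the arm. Ordering the tasks is a precaution, not a correction of a shown breach.

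**Conclusion.** The concern holds in limited form. The blind protects the RAs. It does not extend to QoL-AD ratings, or to other resident scales to the extent that they use staff input. In EIT-4-BPSD homes those informants cannot be blind. That is an inference from their role, since the plan does not describe what staff know in either arm. The main text allows the informant to be someone delivering the intervention.

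A differential shift after training would enter the H1 test directly. An assumed 0.10 SD is about half of d = 0.19. With no true effect, it would raise the chance of a false significant benefit from 2.5% to between 21% and 34%, depending on the analysis variant. These figures rest on the assumed shift and, in points, on the assumed QoL-AD SD.

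A reader might go further and infer that the H1 contrast is biased. The documents show only that it can be. Expectation and better recognition pull in opposite directions and may partly cancel, and nothing in the plan measures either.

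**What to change.** In Procedure for Assessing Outcomes:

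1. Require the staff informant to be a caregiver who is neither the Champion nor a Stakeholder Team member. In EO homes, apply the rule to the Champion named for eligibility. Do not use these people as the designated individual for adverse events.
2. Have RAs finish their own observation and the staff interview before opening the chart or care plan.
3. Describe QoL-AD, and any other staff-informed scale, as collected by a blinded RA from an unblinded informant. Read H1 alongside the outcomes that do not rest on staff report. If Appendix E already gives the source for each measure, refer to it here.

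Cost: a few lines in the protocol and the RA instructions, with no new visits or staff. At some visits the RA must wait for or choose another caregiver, and the blinding claim becomes narrower. Bias is reduced but not removed, because other EIT-4-BPSD staff are also trained.

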Sample Size: Sample size calculation was based on the hypotheses associated with the Effectiveness component of RE-AIM and our prior research.^{8,10,12,22,23,29,77} With regard to facility level outcomes, our prior work resulted in effect sizes of 0.9 for environmental and policy changes.^{22,76,120} With the proposed sample size of 50 facilities, the statistical power for these two measures will be adequate (>.90 for both outcomes based on our analysis plan). For resident level outcomes, person-centered approaches resulted in a small intervention effect (Cohen's $d=0.19$) to maintain or improve BPSD, function, wellbeing or experiencing adverse events.^{8,10,12,22,23,29,77} Given a two-tailed alpha of 0.05, an estimated intra-class correlation coefficient (ICC) between clusters (facilities) of 0.02, a correlation coefficient between repeated measures (baseline, 4 and 12 months) of 0.6, and assuming even dispersion of means, a total sample of 500 residents will provide sufficient power ($\geq .80$) to detect the small effect size for group differences.¹²¹ Our prior research showed a 20% rate of attrition over 12 months.^{8,77} Therefore, we anticipate that a total of 625 residents from 50 nursing homes will be sufficient to demonstrate outcomes. To achieve this sample we will recruit 12-13 residents in each facility.

Setting: Nursing homes will be invited and eligible to participate if they: (a) agree to actively partner with the research team to change practice; (b) have at least 100 beds; (c) identify a RN, LPN or CNA to be the Champion; and (d) are able to access email and websites via a phone, tablet or computer. Recruitment of facilities will be done by mailing invitations to eligible facilities within the two states followed by telephone calls. We will also post invitations on relevant websites (see letters of support). This approach has been used successfully in our prior work.²² Fifty percent of the facilities we invited participated.²² Currently there are 152 nursing homes of appropriate size in Maryland and 439 in Pennsylvania. Given the regulatory climate with respect to dementia care in nursing homes, we are confident we will be able to engage 25 facilities per state.

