Health Status: The *Cumulative Illness Rating Scale (CIRS)*^{135,136} was designed for use with frail nursing facility residents. CIRS will be obtained at baseline. It contains ratings of both illness severity and comorbidity. Residents are evaluated based on 13 organs or systems and a psychiatric/behavioral rating. CIRSSs ratings correlated with medication use and predicted mortality, hospitalization and disability.^{135,136}

Facility and Staff RE-AIM Measures

The Environment Assessment (Effectiveness; Adoption; Maintenance): includes 24 items that impact care of residents with BPSD (e.g., outdoor spaces are available). Items are scored as present or not present and summed. There was prior evidence of inter-rater reliability and validity based on hypothesis testing.^{8 22,23,137}

Policy Assessment (Effectiveness; Adoption; Maintenance): includes 24 items that reflect policies that support behavioral approaches for BPSD (e.g., policies on use of restraints). Items are scored as present or not present and summed. There was prior evidence of inter-rater reliability and validity.^{8 22,23,137}

The Care Plan Checklist for Evidence of Person Centered Approaches for BPSD (Effectiveness; Adoption; Maintenance) is used to evaluate care plans for approaches that address common BPSD (apathy, agitation, inappropriate/disruptive vocalizations, aggression, wandering, repetitive behaviors, resistance to care, and sexually inappropriate behaviors).

Knowledge of Behavioral Interventions For BPSD Test (Implementation; Receipt) is a 10-item multiple choice test that evaluates staff knowledge. Evidence of test-retest reliability was supported with correlations of .92 and validity with significant associations between knowledge and use of behavioral interventions for BPSD.¹³⁸

Use of Behavioral Interventions for BPSD (Implementation; Enactment) is a reliable and valid 8-item observation measure that assesses if nursing assistants implement appropriate interventions to prevent or manage BPSD when interacting with a resident during routine care.¹³⁸

Resident RE-AIM Measures

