Research question: Do facilities exposed to EIT-4-BPSD demonstrate evidence of implementation at 12 months evaluated by Reach, Effectiveness, Adoption, Implementation, and Maintenance (RE-AIM) Criteria?³³

Reach: *To facilities:* Descriptive statistics will describe total number of eligible facilities across both states at the time of recruitment and the percentage of eligible facilities volunteering to participate by state and overall. In addition, we will compare facilities (by state and overall) willing to participate versus those that were not with regard to facility characteristics (e.g., size, profit status). We will also compare facilities expressing a willingness to participate versus those that do not using publically available Nursing Home Compare data.¹⁵² *To staff:* We will evaluate reach to staff in terms of percentage of staff exposed to education (# exposed/total number of staff) in EIT-4-BPSD and EO facilities. *To residents:* Using the Care Plan Checklist for Evidence of Person-Centered Approaches for BPSD we will evaluate the percentage of all residents (using de-identified care plans) living in EIT-4-BPSD facilities that have at least 1 person-centered approach for BPSD.

Effectiveness:

Effectiveness will be based on testing the following *hypotheses*.

H1: Resident level: Residents in EIT-4-BPSD facilities will experience less BPSD, maintain or improve function, have reduced use of psychotropic medications, experience fewer adverse events and have improved quality of life compared to residents in EO facilities.

H2: Facility-level: EIT-4-BPSD facilities will demonstrate improvements in Environment and Policy assessments that support behavioral approaches for BPSD, and will have a greater percentage of residents with behavioral approaches addressed in care plans at 12 months when compared to EO facilities.

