Descriptive statistics including measures of central tendency, dispersion and appropriate visualization approaches (e.g., box plots and spaghetti plots) will be performed on each outcome variable for residents and facilities. This will be done to ascertain distributional characteristics and ensure that the assumptions (e.g., normality) associated with the planned statistical procedures are met. When necessary, transformations will be performed. All analyses will be done using an intent-to-treat philosophy. Baseline characteristics (both resident level and facility level) will be compared between intervention and control groups and the relevant variables (e.g., age) that differ by group will be included as covariates in hypotheses testing. In particular we will utilize constructs known to correlate with BPSD including gender, pain, health status and cognitive and functional impairment. Linear mixed models (LMMs)¹⁵³ for longitudinal data (baseline, 4 and 12 months) will be used to assess the intervention effect on continuous outcomes (i.e., function, behavioral symptoms, and quality of life) accounting for clustering of residents that may occur within the same facility and correlations between repeated measurements of each resident. Mixed-effect Poisson regression [i.e., Generalized Linear Mixed Model

(GLMM)] will be conducted to assess the effect of the intervention on count outcomes (i.e., number of adverse events including number of falls, hospitalizations and emergency room visits, restraint use). The fixed effects included in the models will be treatment group (EIT-4-BPSD versus EO), time (baseline, 4 and 12 months), group-by-time interaction term and the aforementioned relevant covariates (e.g., age). Random effects will include facilities and residents.

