The hypothesis will be tested by evaluating the interaction term for each outcome variable. Similar LMMs will be used to compare changes in facility level measures (i.e., environments, policies) from baseline to 12 months with only facility included as random effects. For each hypothesis, exploratory analyses will be performed to assess model assumptions. Post-analysis diagnostic measures (e.g., residuals) will be explored to assess model fit. All tests will use a 5% significance level. The use of LMM will provide flexibility with regard to assumptions related to the covariance structure of the residuals and the presence of missing data for the repeated measures.¹⁵⁴ Missing data. In prior research we had 20% rate of attrition at the resident level and 10% of facilities.^{22,23} If there is significant dropout, we will identify baseline characteristics that differ between persons or facilities that drop out. Maximum likelihood methods will be used for primary analyses, which address non-informative dropout (missing at random [MAR]). If "informative" dropout appears possible, we will consider sensitivity analyses that involve adding these relevant baseline covariates to make the MAR assumption more plausible.¹⁵⁵ Qualitative data will be collected to inform effectiveness outcomes.

Adoption: Staff Adoption: Descriptive statistics will be done to evaluate the number of Internal Champions and Stakeholder team members participating in initial face-to-face training and monthly meetings among the 25 facilities randomized to EIT-4-BPSD. We will also consider improvement in scores on the Use of Behavioral Interventions for BPSD measure at each testing time point as evidence of adoption among staff. Facility Adoption: Facility adoption will be based on changes in environments, policies, and care plans of residents at 4 and 12 months post implementation of EIT-4-BPSD such that there is at least 1 item changed in each assessment area. Further we will describe differences among EIT-4-BPSD facilities that demonstrate adoption (based on changes in environments, policies and care plans) early (the first 4 months) versus late adopters (between 5-12 months) versus those that are non-adopters (no change by 12 months). Predictors such as facility characteristics will be compared across the three potential times of adoption (early, late, nonadopters).

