Maintenance: Long term Attrition: We will track facilities that withdraw from the study within 12 months (as well as reasons for attrition). We will compare EIT-4-BPSD facilities with EO facilities to determine if there is a differential rate of attrition. Maintenance of environment and policy changes and inclusion of person-centered approaches for BPSD in care plans will be examined at 24 months post implementation of EIT-4-BPSD. Evidence of maintenance will be based on maintaining or improving Environment and Policy assessments and percentage of residents with evidence of person-centered approaches for management or prevention of BPSD in their care plans. LMMs will be used to compare changes in facility level measures from baseline to 24 months with facility included as random effects. Time will be included and recorded accordingly. Comparison of outcomes at 12 and 24 months will be examined to determine maintenance over that time period.

Primary Aim 2: Evaluation of the Feasibility, Utility and Cost in EIT-4-BPSD Facilities

Using descriptive and qualitative data from focus groups (held following the intervention) we will evaluate use of the EIT strategy and our participatory implementation process with the stakeholder team and additional facility staff. We will determine the cost of the implementation process using an activity-based costing method.

Aim 2: To evaluate the use of EIT and our participatory implementation process.

Findings will be descriptive and considered at the individual facility level and across all treatment facilities. Data will include a summary of information obtained during the intervention including: (1) ideas generated from the Brainstorming sessions¹⁵⁶; (2) themes identified in the Affinity Diagrams; and (3) "drivers" identified to overcome challenges to implementing person-centered behavioral approaches to BPSD via implementation of the EIT-4-BPSD (Interrelationship Diagraphs). We will quantify similarities across facilities to note the most common themes and drivers identified and establish best practices. We will also have facilities evaluate their goal achievement at 12 months (Appendix B).

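### In the supplied text, death is not among the adverse events compared between arms, so H1's adverse-event claim could be reported without any comparison of resident deaths

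*Combined protocol and SAP*

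**What the plan says.** - **Definition.** Under Resident RE-AIM Measures, Adverse Events (Effectiveness): "Adverse events will include falls and transfers to hospitals or emergency rooms and physical restraint use".
- **Analysis.** Data Analysis, Effectiveness, assigns to a mixed-effect Poisson model the "number of adverse events including number of falls, hospitalizations and emergency room visits, restraint use". No offset for time at risk is stated.
- **Hypothesis.** H1 expects residents in EIT-4-BPSD homes to "experience fewer adverse events and have improved quality of life compared to residents in EO facilities".
- **Resident loss.** Sample Size: "Our prior research showed a 20% rate of attrition over 12 months". If dropout is significant, the missing-data paragraph says "we will identify baseline characteristics that differ between persons or facilities that drop out". It also says "Maximum likelihood methods will be used for primary analyses, which address non-informative dropout (missing at random [MAR", and it allows sensitivity analyses that add baseline covariates if informative dropout looks possible.
- **Facility loss.** Under Maintenance: "We will track facilities that withdraw from the study within 12 months (as well as reasons for attrition". Rates of facility attrition are then compared between arms.
- **Mortality.** The only mention is a validity statement about the illness rating scale in the Health Status paragraph: "CIRSSs ratings correlated with medication use and predicted mortality, hospitalization and disability".

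**The concern.** H1 makes a comparative statement about adverse events in cognitively impaired long-stay residents, a fifth of whom are expected to be lost within a year. Death is the most serious event that can befall them, and it is neither in the list of events nor a named category of loss.

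This matters in two ways. First, a resident who dies in the nursing home without a fall or transfer adds nothing to the adverse-event total, and one who dies after a transfer counts the same as one who recovers. An arm could show fewer falls and transfers while the reader is told nothing about deaths in either arm. Second, death ends the period in which the listed events can happen. With no offset stated, shorter observation lowers a resident's count. An offset would correct the second problem but not the first, because the death itself would still not be compared.

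**Working it through.** **1. Where death could enter the comparison.** Set side by side:

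| Place | What it covers | Death or resident's reason for loss? |
|---|---|---|
| Adverse Events definition | Falls, hospital or ER transfers, restraints | Not named |
| Poisson count list | The same events | Not named |
| Missing data | Baseline characteristics of those who leave; likelihood methods under MAR | Not named |
| Maintenance | Facility withdrawal and reasons | Facilities only |
| Strengths and Limitations | Resident loss answered by oversampling | Not named |

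The definition's verb leaves room for other events, but the analysis list adds none.

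**2. The plan's own figure.** Inputs from Sample Size: 500 evaluable residents, 20% attrition. 500 / (1 − 0.20) = 625, which reproduces the stated target. Expected losses: 0.20 × 625 = 125.

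**3. What a mortality comparison could show.** The documents give no death rate, so the share of the 125 losses due to death is an assumption, taken as 25%, 50% or 75%. Arms are taken as equal (25 facilities each, 312.5 residents). The design effect uses the plan's ICC of 0.02, which was given for the resident-level outcomes and is borrowed here for death, with 625 / 50 = 12.5 residents per facility: 1 + (12.5 − 1) × 0.02 = 1.23.

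Approximate 95% factor for the mortality ratio, with d deaths per arm: exp(1.96 × √(1.23 × 2 / d)). For the risk difference, the half-width is 1.96 × √(2p(1 − p) × 1.23 / 312.5).

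| Share of losses | Deaths (per arm) | Mortality p | Factor, no clustering | Factor, design effect 1.23 | Risk difference half-width |
|---|---|---|---|---|---|
| 25% | 31 (15.6) | 5% | 2.02 | 2.18 | 3.8 points |
| 50% | 63 (31.3) | 10% | 1.64 | 1.73 | 5.2 points |
| 75% | 94 (46.9) | 15% | 1.50 | 1.57 | 6.2 points |

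On the same design effect, 80% power would need differences such as 10% against 18.7%, or 15% against 25.0%.

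**4. How far deaths could shift the event counts.** Assume deaths spread evenly over 12 months, the same event rate while alive in both arms, partial counts kept, and no offset. Mean time at risk is then 1 − p/2 of a year. With 10% mortality in EO and 20% in EIT-4-BPSD, the apparent event ratio is (1 − 0.10) / (1 − 0.05) = 0.90 / 0.95 = 0.947. With 15% against 20%, it is 0.90 / 0.925 = 0.973. With equal mortality it is 1.000.

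**The case against.** The strongest objection is that the supplied file is incomplete. It refers to a Human Subjects section, to Appendix E for the source and timing of each measure, and to Appendix F for the measures themselves; none is supplied. Deaths and resident withdrawals may be recorded there. A reader might infer from the listed events that deaths go unrecorded, but the documents do not support that. The sentence on reasons for attrition sits in a facility-level part of the plan. It shows that facility reasons are tracked, not that resident reasons are ignored. What stands is narrower: the supplied analysis section plans no comparison of resident deaths and no account of resident losses by reason.

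Second, the events are openly labelled as effectiveness outcomes in a Hybrid III trial, and falls and hospital transfers are ones the team's earlier work reported reducing. The meaning of H1 can be read from the list. That is fair, but it does not remove the need to see deaths next to a claim of fewer adverse events.

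Third, a reader might infer that extra deaths could by themselves produce an apparent benefit. Step 4 argues against this: even a doubling of mortality from 10% to 20% moves the ratio only to about 0.95, and the documents do not say how partial counts are handled.

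Fourth, the sensitivity analyses for informative dropout go beyond a plain MAR analysis. They only add baseline covariates, however, so they do not compare deaths.

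**Conclusion.** The point holds for the outcome definitions and analysis plan as supplied. Followed as written, they allow a conclusion of fewer adverse events with no comparison of resident deaths and with counts that death can cut short. This limits one part of H1 and does not invalidate the trial.

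The missing comparison concerns an unknown share of about 125 expected losses. At the assumed shares, a mortality ratio would be known only to within a factor of about 2.2, 1.7 or 1.6 either side, so a large imbalance could be shown and a moderate one could not. These limits rest on equal arms, a borrowed ICC and the assumed death shares. It would go too far to say that any particular part of the 20% attrition is death, because the documents do not break that figure down. The distortion of the fall and transfer counts is a secondary issue and likely small.

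**What to change.** - In the Adverse Events entry, add death with its date. Record for each resident lost the reason: death, discharge or transfer, withdrawal, or withdrawal of the facility.
- In Data Analysis, Effectiveness, report deaths and reasons for loss by arm, with a facility-clustered estimate and 95% confidence interval for mortality, shown beside the fall and transfer results.
- Use log time at risk as an offset in the Poisson models, and state that events before a resident leaves are kept.
- If the Human Subjects section or the appendices already provide for recording deaths, refer to them from the analysis section.

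Making the H1 conclusion formally conditional on the mortality result is more than the point requires; showing the two together is enough.

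The cost is one date and one reason field from the medical chart that the research assistants already use at 4 and 12 months, plus one further estimate. The sample size and visits do not change. The downsides are an imprecise mortality estimate, to be reported as such, and possibly incomplete follow-up for discharged residents and for withdrawn facilities (10% of facilities in the team's prior research).
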